5.1 Analysis Populations

One control population will be considered in primary analyses: the historical control population. The historical control population includes all subjects who attended ChristianaCare during the eligibility period and who satisfy all eligibility criteria.

The historical control arm will be the control population for primary and alternative analysis of the primary, secondary and exploratory endpoints.

Seven subject populations will be considered in the analyses: an Intent-to-Treat (ITT) population, a modified ITT population, a completer(s) population, a compliant completers population, a non-intervention completers population and a safety population. The completers, compliant completers, non-intervention completers and modified ITT populations are subsets of the ITT population.

The ITT population includes all historical subjects selected and all prospective patients enrolled regardless of whether or not the co-primary outcomes were observed, or in the prospective arm, any PreTRM test result has been generated or intervention consent has been signed. Subjects with missing outcomes will be handled as described in the missing data sensitivity analyses.

The modified ITT (mITT) population includes all subjects for whom both co-primary outcomes are known; and who have either been selected for the historical control group, received a not-higher-risk PreTRM® test result, or consented to and initiated treatment before 24^{0/7} weeks gestation after receiving a higher risk PreTRM® test result.

The completers population includes subjects for whom both of the co-primary outcomes are known, and, in the prospective arm, for whom a PreTRM® test result was generated.

The compliant completers population includes ITT subjects who have missed no more than 20% of daily doses for both low-dose aspirin and vaginal progesterone, and participated in weekly care management calls with no more than 20% missed weeks.

The non-intervention completers population includes all ITT subjects who received a higher-risk PreTRM® test result but neither consented to nor initiated treatment before 24^{0/7} weeks gestation.

The safety population includes all eligible subjects who gave consent to participate in the study and attempted a blood draw for the PreTRM® test, regardless of receipt of study interventions.

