As an exploratory analysis, a test of the proportional odds assumption for NMI data will be conducted. If the proportional odds assumption does not hold, we will examine the data using a set of separate logistic regressions or partial proportional odds models, to explicitly see how the odds ratios for the explanatory variables vary at the different thresholds. Alternatively, we will also apply the generalized logit model, which treats the response as nominal (unordered) rather than ordinal and has a full set of parameters for each generalized logit. We will then compare the results from proportional, fully nonproportional, and partial proportional odds models fitted to data.

As exploratory analyses, the primary analysis will be replicated, with the modification that the analysis will be restricted to prospective subjects with at least one propensity-matched control, and historical controls will be restricted to those propensity-matched to prospective subjects. At most 4 historical controls will be matched to each prospective subject. Matching algorithms will be chosen from among nearest neighbor matching, caliper matching with comparison units within a certain width of the propensity score of the treated units get matched, where the width is generally a fraction of the standard deviation of the propensity score; Mahalanobis metric matching in conjunction with propensity score matching (PSM), stratification matching, difference-in-differences matching (kernel and local linear weights), or exact matching. The matching method will

be chosen by the distribution of the propensity scores and the balance status of baseline characteristics.

As exploratory analyses, the primary and alternative analyses will be replicated using the ITT population. Subjects with missing data for required variables will be excluded from the analyses. To test if covariates are known to be misclassified under some approaches, an “intention to treat” analysis will be conducted that assumes that each participant continues to be exposed once they have received an initial treatment. Originally used in the analysis of randomized trials, this approach has been used in this hybrid study. It can be worthwhile to do a sensitivity analysis on studies that use an “intention to treat” approach to see how different an “as treated” analysis would be even if intention to treat is the main estimate of interest.

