As exploratory analyses, the primary and alternative analyses will be replicated using the completers population with treatment covariates. Covariates for treatment modalities inclusive of use of aspirin or progesterone, will be included in the analyses if showing record of use between LMP and delivery in both the prospective arm and historical controls. Subjects with missing data for required variables will be excluded from the analyses. Subjects in the higher-risk group accepting interventions will be compared to non-intervention completers and to historical controls using descriptive statistics as described above. If use of any treatment is significantly associated with variables specified for the alternative analysis, this analysis will be repeated with inclusion of such variables as covariates in the analysis. Subjects with missing data for required variables will be excluded from this analysis.

As an exploratory analysis, the primary and alternative analyses will be replicated using the compliant completers population plus the not-higher-risk group as the preterm prevention arm for comparison to historical controls. Additional subgroup analysis of the compliant completers population will apply the primary, secondary and exploratory endpoints to subjects compliant with each component of the intervention versus all other compliant completers, and versus non-intervention completers. If compliance with any

treatment is significantly associated with variables specified for the alternative analysis, this analysis will be repeated with inclusion of such variables as covariates in the analysis. Subjects with missing data for required variables will be excluded from this analysis.

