6.1 Potential bias in the hybrid study

In this study, it is crucial to address selection bias, epoch bias, bias from self-selection of compliant completers in the higher-risk group, as well bias due to COVID-19 / SARS-CoV-2 exposure in the last ~400 subjects. Selection bias is the bias introduced by the selection of individuals, groups or data for analysis in such a way that proper randomization is not achieved, thereby ensuring that the sample obtained is not representative of the population intended to be analyzed. In this study, prospective intervention group and historical cohort study group are not allocated through randomization, therefore selection bias may be one of the important issues to be addressed. As the prospective arm and historical controls received care in different periods, epoch effects from trends in patient care and in public health may also prove an important source of bias. Finally, incomplete acceptance of interventions by some higher risk subjects in the prospective arm provides a source of bias that cannot be directly adjusted, as no higher risk group defined by PreTRM® risk score is present amongst the historical controls. Bias due to comparison of historical controls from a pre-pandemic period to prospective subjects reaching term during the SARS-CoV-2 pandemic has been ameliorated by restriction of the study to subjects reaching term before detection of the first SARS-CoV-2 positive case in Delaware.

Bias from any source will cause the distortion of a statistical analysis. Bias can have varying effects, and the magnitude of its impact and the direction of the effect are often hard to determine. If bias is not taken into account, the results and conclusions of the study may be false or misleading. Therefore, it is necessary to consider the sources of bias in the outcomes analysis.

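### The completers replication is planned only with aspirin and progesterone use as covariates, so its arm coefficient does not estimate the effect of the screen-and-treat strategy and can be biased in either direction

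*SAP*

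**What the plan says.** Section 5.4 runs the primary and alternative analyses in the mITT population. That population leaves out higher-risk women who did not consent to and start treatment before 24 0/7 weeks. The completers population in section 5.1 brings them back: in the prospective arm it needs known co-primary outcomes and a woman "for whom a PreTRM® test result was generated".

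Section 5.7 then states that "the primary and alternative analyses will be replicated using the completers population with treatment covariates". It goes on: "Covariates for treatment modalities inclusive of use of aspirin or progesterone, will be included in the analyses if showing record of use". The window for that record runs from LMP to delivery, and use must be on record in both groups. Both drugs belong to the study intervention: section 5.1 defines compliant completers as women who "missed no more than 20% of daily doses for both low-dose aspirin and vaginal progesterone" and who kept up the weekly care-management calls.

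If treatment use is associated with the alternative-analysis variables, "this analysis will be repeated with inclusion of such variables as covariates in the analysis". That adds baseline terms and does not take the treatment terms out. The include-or-omit covariate sensitivity analysis in section 5.7 is confined to mITT, and the unadjusted analysis replicates the primary, hence mITT, analysis. No completers model without treatment covariates is written down.

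**The concern.** The study asks whether testing, followed by treatment of higher-risk women, improves neonatal outcomes over usual care. In the prospective arm, drug use after the result is a step in that strategy. Conditioning on it has two consequences.

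- It takes part of the strategy's own pathway out of the arm effect.
- It breaks the comparability of the groups. Prospective non-users have lost the higher-risk women who took treatment, while control non-users still include the equivalent women. Users differ as well: prospective users are mostly women picked by the score, control users are women given the drugs in routine care.

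The other covariates cannot repair this. Section 6.1 concedes that "no higher risk group defined by PreTRM® risk score is present amongst the historical controls", and the lists in section 5.3 contain neither prior preterm birth nor cervical length.

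At stake is how one exploratory result is read. Completers restore the decliners whom mITT drops, so a reader will naturally treat this replication as a check on the mITT result.

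**Working it through.** The SAP gives no figure for this analysis, so there is none to reproduce. The check asks what the drug term does to the arm odds ratio (OR) when the two cohorts are identical and treatment does nothing.

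**Inputs from the SAP (sections 4 and 5).** 1,453 prospective women and 10,000 controls; 34% higher-risk; 55% compliance among them, used here as drug uptake; NMI ≥ 3 in 3.6% of controls; one-sided test, taken at 0.05.

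**Assumptions not in the SAP.** Risk ratio of higher-risk against other women k = 2–3; background drug use u = 2–10% in both cohorts; risk ratio of background users against non-users r = 0.7, 1, 2 or 3; uptake unrelated to other risk.

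**Model.** Logistic regression of NMI ≥ 3 on arm, without and with a single drug-use indicator, fitted to expected cell counts. Baseline risk is b = 0.036 / [(1 + 0.34(k − 1)) × (1 + u(r − 1))]. The false-positive rate is Φ(−1.645 − z), with z the expected Wald statistic for arm.

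**One case in full: k = 2, u = 5%, r = 3.**
- b = 0.036 / (1.34 × 1.10) = 0.0244.
- Control non-users: 0.0244 × 1.34 = 3.3%. Control users: three times that, 9.8%.
- Prospective women not on study drug: 66% test-negative plus 34% × 45% = 15.3% higher-risk decliners, 81.3% in all. Non-user risk: 0.0244 × (0.66 + 2 × 0.153)/0.813 = 2.9%.
- Prospective users: 34% × 55% = 18.7% on study drug, at risk 0.0244 × 2 × 1.10 = 5.4%, plus 81.3% × 5% = 4.1% background users, at risk 3 × 2.9% = 8.7%. Weighted risk 6.0%.
- Both cohorts have 3.6% overall, so the arm-only OR is 1.00. Within non-users the OR is about 0.88, and within users about 0.58. The pooled adjusted OR is 0.77.
- In 4,000 simulated trials the one-sided test rejected in 4.7% without the drug term and 50% with it.

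**Range with no true effect (k = 2–3, u = 2–10%).** The arm-only OR is 1.00 throughout.

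| Background-user risk ratio r | Adjusted arm OR | One-sided false positives |
|---|---|---|
| 0.7 | 0.94–1.03 | 3–11% |
| 1 | 0.91–0.98 | 6–14% |
| 2 | 0.83–0.86 | 24–31% |
| 3 | 0.76–0.78 | 44–55% |

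If neither the score nor background use marks risk (k = 1, r = 1), the adjusted OR is 1.00 and the rate 5%.

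**With a real drug effect (OR 0.5 among all users in both cohorts, u = 5%).**

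| k | r | Arm OR without drug term | Arm OR with drug term |
|---|---|---|---|
| 1 | 1 | 0.91 | 1.00 |
| 2 | 1 | 0.86 | 0.93 |
| 2 | 3 | 0.87 | 0.81 |
| 3 | 3 | 0.85 | 0.77 |

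In the first row the benefit vanishes, in the second it shrinks, and in the last two it is overstated. If instead treatment halves risk only in women treated under the protocol and r = 1, the adjusted OR is 0.82–0.87 against 0.83–0.86 unadjusted, which is almost no change.

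**The case against.** Four points on the other side carry weight.

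**A cleaner check is planned.** Section 5.7 also states that "the primary and alternative analyses will be replicated using the ITT population", with no treatment covariates and with women with missing data excluded. It includes higher-risk decliners and differs from completers mainly by women without a test result. A reader might infer that mITT has no sound whole-cohort check; the SAP does not support that.

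**The purpose may be different.** The abstract says exploratory analyses compare accepters with non-accepters and address individual components, and section 5.7 speaks of an as-treated contrast. Nothing says that this arm coefficient is meant as the strategy effect. This stands as a reason to relabel. It does not rescue the model as a replication of the primary analysis, which is how the SAP describes it, nor does it make the arm coefficient a component effect.

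**The direction is not fixed.** A reader might infer that the model adjusts the intervention away, or that it manufactures benefit. The SAP gives neither the background use nor its risk, and either result, or neither, can follow. The 44–55% error rates need background users at three times the risk. Care-management calls are not named as a covariate, so part of the bundle may stay in the arm effect.

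**The calculation is simplified.** The plan uses weighted ordinal regression for NMI, Cox regression for length of stay, possibly one term per drug, baseline covariates and, in the alternative analysis, inverse-probability weighting. Added baseline variables would absorb some indication-driven risk, though not the score. The figures illustrate the mechanism and do not predict the planned test's error rate.

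**Conclusion.** The point holds for this one exploratory analysis. As written, the only completers replication conditions on drug use that is largely a consequence of testing in one cohort and routine care in the other, so its arm coefficient should not be read as the effect of screening and treating. The possible distortion is not trivial: with no true effect the illustrated OR runs from 1.03 down to 0.76, depending on assumed inputs, chiefly the risk of background users. The terms also enter only if use is recorded in both groups, which is likely with about 10,000 controls. The Holm-controlled co-primary tests are unaffected, and the ITT replication will stand beside this result. The consequence is a misleading exploratory estimate and does not threaten the trial's main conclusion.

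**What to change.** In section 5.7:

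1. Run the completers replication with the primary- and alternative-analysis covariates and no treatment covariates, and name that the completers result.
2. In any prospective-versus-historical model, restrict a drug covariate to use recorded before the blood draw, the standard that section 5.3 sets for its baseline covariates. Where the record cannot show that timing, leave the term out.
3. If the treatment-adjusted model is kept, label it a component or as-treated analysis and state that its arm coefficient is not the effect of screening.

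The cost is one additional model and a few lines of SAP wording. In the simulated no-effect cases, the model without the drug term rejected in 4.4–4.7% of trials at one-sided 0.05, so the change restores the nominal size.

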The AVERT study addresses an enormous obstetrical problem having a large unmet need with the use of a novel risk assessment tool (PreTRM®) and established multimodal interventions administered within the single ChristianaCare hospital network. However, there are several potential limitations to the AVERT study. Comparisons to historical controls can be susceptible to selection bias and epoch effects. Subjects who don't accept interventions may add self-selection bias. As well, AVERT is subject to a research halt due to the spread of SARS-CoV-2, avoiding a pandemic epoch effect while restricting study size.

This statistical analysis plan addresses the study objective of evaluation of the PTB prevention strategy while overcoming potential study limitations. The original endpoints are replaced with more powerful endpoints aligned to the study size and faithful to the study's goal of reducing adverse outcomes. The primary analysis is in a modified ITT population enabling comparison of the fully consented PTB prevention strategy population to a population who received standard care. To adjust for any bias in consent to intervention, exploratory analyses compare subjects accepting and not accepting interventions, and address the efficacy of individual intervention components.

An estimated 1,453 prospective subjects reached a gestational age of $37^{0/7}$ weeks before local spread of SARS-CoV-2 in Delaware and the associated shut-down of non-COVID-19 research at ChristianaCare. Approximately 10,000 historical controls were selected

from a period of about 2 years immediately prior to study initiation. The study design shows at least 86% power for 5% alpha shared across two co-primary endpoints: neonatal morbidity and mortality index and neonatal length of total hospital stay.

The funder, Sera Prognostics, will remain blinded to all clinical data until a formal communication of topline results from this analysis is made.

Background: Preterm birth (PTB) remains the leading cause of neonatal mortality and long term disability throughout the world. Recently treatments early in pregnancy such as progesterone, cervical support and maternal support have been demonstrated to delay delivery amongst at risk women. Nonetheless, the majority of women who are at risk are not identified using current screening modalities.

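### For aspirin, progesterone and care-management calls, the exploratory component-compliance contrast in SAP 5.7 has an empty comparison group, because SAP 5.1 requires compliance with all three

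*SAP*

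**What the plan says.** Section 5.1 (Analysis Populations) defines compliant completers by criteria joined with an and. Members are those who "missed no more than 20% of daily doses for both low-dose aspirin and vaginal progesterone" and who also "participated in weekly care management calls with no more than 20% missed weeks".

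Section 5.7 (Exploratory Analyses) first uses this group, together with the not-higher-risk women, for a full comparison with historical controls. It then adds a further step: "Additional subgroup analysis of the compliant completers population will apply the primary, secondary and exploratory endpoints". Two contrasts are named for this step. The first is of "subjects compliant with each component of the intervention versus all other compliant completers". The second sets the same component-compliant women against the non-intervention completers. Section 5.1 describes the latter as women who "received a higher-risk PreTRM® test result but neither consented to nor initiated treatment before" 24 0/7 weeks.

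The Executive Summary in section 2 gives the purpose. Among other things, the exploratory analyses are to "address the efficacy of individual intervention components".

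**The concern.** The population is selected on the same variable that the analysis then uses to split it. If entry requires compliance with aspirin, progesterone and calls, no member can be non-compliant with any of them, and there is nobody to compare with.

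Two things are at stake. First, this is the only analysis in the SAP that addresses individual components through adherence, and it cannot be carried out for the three components that have an adherence rule. An analyst who finds the group empty must choose another population or comparator with the data in hand, which defeats the purpose of prespecifying it. Second, the contrast with non-intervention completers can be run and sits under a component heading. Its result could be reported as an aspirin effect or a progesterone effect when it reflects compliance with all three together.

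**Working it through.** The SAP gives no sample size, power or event count for this analysis, so there is no figure to reproduce. The check is logical.

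**Inputs.** Section 5.1: rule A (aspirin, at most 20% of daily doses missed), rule P (progesterone, the same) and rule C (calls, at most 20% of weeks missed), with entry requiring A and P and C. Section 5.7: the analysis population is the compliant completers, and the split is compliant with a given component against all others in that population.

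**Step 1: patterns.** Three yes/no criteria give 2 × 2 × 2 = 8 patterns. Only the pattern yes/yes/yes satisfies section 5.1, so 1 of 8 enters.

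**Step 2: split the population as section 5.7 directs.**

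| Component | Patterns compliant | Patterns in the other group |
|---|---|---|
| Aspirin | 1 | 0 |
| Progesterone | 1 | 0 |
| Calls | 1 | 0 |

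The other group is empty for each component, whatever the number of women. Reading the word each as every does not help with these three: all members then fall on the compliant side.

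**Step 3: the second contrast.** The women compliant with aspirin, with progesterone and with calls are the same set in this population. Set against one fixed comparator, the three contrasts are one contrast and return one estimate.

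**Step 4: the conditional repeat.** Section 5.7 adds a rerun with further covariates if compliance with a treatment is associated with variables from the alternative analysis. Inside this population compliance with the three components does not vary, so that condition cannot be assessed there.

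**Step 5: would a wider population work?** Among women compliant with at least one component there are 7 patterns, and each component divides them into 4 compliant and 3 non-compliant. Once the joint entry rule is relaxed, both sides can be populated.

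**The case against.** **The bundle may have other components.** This stands as a limit. The SAP refers to a multimodal protocol that is not at hand and does not list every component. Compliant completers could differ on a component outside the three rules. A reader might infer that they comply with every part of the bundle; the SAP supports this only for the three with a stated rule.

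**The words about both drugs could mean doses pooled across them.** With equal numbers of scheduled doses, a woman missing 0% of one drug and 40% of the other has a pooled figure of (0 + 40)/2 = 20% and would qualify. The drug comparators could then be non-empty. The wording does not favour this reading, and the calls comparator stays empty under it.

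**There is another route to component effects.** This stands in part. Section 5.7 also repeats the primary and alternative analyses in the completers population with covariates for treatment use, including aspirin and progesterone. Completers need not be compliant, so partly compliant women are included. A reader might infer that the plan has no means of addressing components; that would be wrong. But this route models recorded use rather than adherence, requires use in both arms, and does not clearly cover calls.

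**The comparator is not untreated.** This is correct. Non-intervention completers are defined only by no consent and no initiation before 24 0/7 weeks. Later treatment, or use outside the study, is not excluded, so they should not be described as women who took nothing.

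**The matter is minor.** The analysis is exploratory and carries no alpha, and an empty group would be noticed at programming. That limits the consequence, but it does not make the rule executable.

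**Conclusion.** The point holds for aspirin, progesterone and calls. The section 5.7 contrast with other compliant completers has a comparator of size zero for each, and the contrast with non-intervention completers gives a single estimate for joint compliance, not a component effect. This rests on the plain reading of section 5.1, in which each drug is judged separately, and on the three components for which the SAP sets a rule.

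The reach is one exploratory analysis. The co-primary and secondary tests do not depend on it.

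It is tempting to size the loss from section 4: 1,453 × 0.34 = about 494 higher-risk women, and 494 × 0.55 = about 272 treated. The SAP does not support that use. Section 4 describes the 55% as compliance with interventions, not initiation, and gives no count of partly compliant women. Only the logical zero is established.

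**What to change.** Reconcile sections 5.1 and 5.7:

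- Run the component contrast in higher-risk women who consented to and initiated treatment before 24 0/7 weeks, that is, the treated higher-risk part of the mITT population.
- Classify each woman separately on aspirin, progesterone and calls with the existing 20% rule, and compare compliant with non-compliant women for each component.
- Adjust for the other components only if numbers allow.
- Keep compliant completers for the full-bundle comparison, and describe their contrast with non-intervention completers in those terms.
- Label the component results hypothesis-generating.

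The cost is SAP wording. Adherence by component is already needed to apply section 5.1, so no new data are required. The limitation is precision and confounding: adherence is self-selected and correlated across components, and events are few. Section 4 expects NMI of 3 or more in 2.0% to 2.3% of the prospective arm, that is 1,453 × 0.020 = 29 to 1,453 × 0.023 = 33 in the whole arm, of which the treated higher-risk women would contribute only a part.
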